All subjects will be scanned on standard MDCT scanners (Definition Dual Source/Definition Flash, Siemens Medical Solutions, Erlangen, Germany; or Brilliance 256-slice, Philips Medical Systems, Best, The Netherlands) after administration of iodinated contrast (80-100 mL of Ultravist 370) at 4-5 mL/s followed by 30-50 mL of normal saline. Bolus tracking technique using a region of interest in ascending aorta will be used, and scanning (from the carina to the mid left ventricle) will be performed initiated in the craniocaudal direction during a single inspiratory breath-hold. Spiral data will be acquired with retrospective electrocardiogram gating using the following parameters: gantry rotation time=270-330 ms; beam collimation ranging from 128 x 0.6 mm to 32 x 0.6mm; tube voltage=100-120 kVp; tube current adjusted per patient weight; and beam pitch of 0.2-0.5. Electrocardiogram-based tube current modulation will be used for all patients, with maximum current turned on between 30-70 % phases of the cardiac cycle (hence maintaining image quality during the systolic phases). 4dimensional images will be reconstructed during 10 phases of the cardiac cycle with a section thickness of 0.75 mm. Radiation in the study sample will typically be < 12 mSEV.

Leaflet motion analysis

Based upon the 4D MDCT data, we will attempt to measure leaflet tip thickness. In addition, leaflet motion will be judged as normal, mildly reduced (<50% reduction in motion), moderately reduced (50 to 70% reduction), severely reduced (>70% reduction), or immobile (lack of motion of at least one valve leaflet). For the purposes of analysis, leaflet motion will be considered reduced if it is moderately reduced, severely reduced, or immobile. The 4D CT scans will be interpreted by a reviewer who is blinded to the anticoagulation/antiplatelet regimen for the patient.

Crossovers

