Patients who are randomized to an aspirin group and who develop a new indication for periprocedural anticoagulation (e.g. perioperative atrial fibrillation) will be crossed over into the warfarin group. Patients who are randomized to a warfarin group who develop contraindications to warfarin will be crossed over to the aspirin group. Patients who are randomized to an aspirin group who develop overt leaflet thrombosis, as detected by clinical standard of care imaging may be treated with warfarin at the discretion of the treating physician. However, the physicians will be blinded to the results of the 4D MDCT scan till the completion of the study.

Funding

Funding will be provided by the [name] treasury fund (000000991924, T56338).

Adverse Events and Independent Medical Safety Officer

Adverse events will be reported directly to the IRB.

An Unanticipated Problem Involving Risks to Participants or **Others** is any event that (1) is unforeseen, (2) caused harm or placed a person at increased risk of harm, and (3) is related to the research procedures.

An Adverse Event (AE) defined for this pilot study is any untoward or unfavorable medical occurrence related to structural valve deterioration, bleeding, stroke, TIA or MI.

A Serious Adverse Event (SAE) is any adverse experience that results in any of the following outcomes:

- 2 death
- a life-threatening experience
- ☐ inpatient hospitalization or prolongation of existing hospitalization
- a persistent or significant disability/incapacity
- ② a congenital anomaly/birth defect
- Important medical events that may not result in death, be life-threatening, or

require hospitalization may be considered a serious adverse drug experience when, based upon appropriate medical judgment, they may jeopardize the patient or subject and may require medical or surgical intervention to prevent one of the outcomes listed in this definition.

The independent Medical Safety Officer will routinely review all deaths, SAEs, adverse events and imaging. The medical safety officer will be separate and independent from clinical staff or anyone responsible for patient care.

Statistical Analysis

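### The 4D MDCT blind is worded to cover every scan result; limit it to the leaflet reads and write down how other important findings reach the treating physician

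*Combined protocol and SAP*

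**What the plan says.** All places are in the combined protocol and SAP.

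- **Crossovers.** An aspirin-arm patient with overt leaflet thrombosis on standard-of-care imaging may be given warfarin at the treating physician's discretion. The next sentence is: "However, the physicians will be blinded to the results of the 4D MDCT scan till the completion of the study".
- **Contrast enhanced 4D MDCT.** Every subject has a contrast scan, with the field given as "scanning (from the carina to the mid left ventricle".
- **Leaflet motion analysis.** Two CT reads are defined. One is thickness: "Based upon the 4D MDCT data, we will attempt to measure leaflet tip thickness". The other is a graded judgement of leaflet motion, from normal to immobile. On the reader: "The 4D CT scans will be interpreted by a reviewer who is blinded to the anticoagulation/antiplatelet regimen for the patient".
- **Adverse Events and Independent Medical Safety Officer.** "The independent Medical Safety Officer will routinely review all deaths, SAEs, adverse events and imaging". Also: "The medical safety officer will be separate and independent from clinical staff or anyone responsible for patient care".
- **Follow up.** The CT and a TTE are done at 4-6 weeks. After that come phone calls at 6, 9 and 12 months, each with a window of 7 days either way. They ask about medications, bleeding, stroke, TIA and MI, and collect INR and imaging results.

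**The concern.** The blind exists to stop the leaflet reads from steering anticoagulation. As written it reaches further, because it covers whatever the scan shows. A contrast CT of this field shows more than three leaflets, and the sentence makes no exception for a finding that needs action.

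If staff follow the sentence to the letter, an actionable non-leaflet finding noticed by the CT reader or the safety officer could stay with that person. The TTE at the same visit is not blinded, but it examines the heart and valve and does not replace the CT for the rest of the field. Patient safety is what is at stake. The leaflet blind itself is sound, and nothing here argues for weakening it.

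**Working it through.** The plan states no figure on this point, so there is none to reproduce. The check is a comparison of the texts, followed by simple date arithmetic.

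**1. Scope of the blind against what needs blinding.** The Crossovers sentence refers to the results of the scan without qualification. Leaflet motion analysis defines only motion grade and tip thickness. The blind as worded is therefore wider than the reads it protects.

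**2. Is there a written route for anything else?**

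| Possible route | What the protocol gives | Does it reach the treating physician? |
|---|---|---|
| CT reader | Blinded to regimen; reads leaflets | No reporting duty stated for other findings |
| Medical Safety Officer | Routinely reviews imaging; independent of the care team | No onward step stated |
| Adverse-event reporting | Limited to structural valve deterioration, bleeding, stroke, TIA or MI; goes to the IRB | An incidental CT finding is outside the definition on its face |
| Unanticipated problem | Must be related to the research procedures | Same |
| Phone calls | Collect information from the patient | Not described as passing CT results on |

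The protocol calls the TTE clinically indicated. It does not say this of the CT, so a routine clinical CT report cannot be presumed.

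**3. Length of the rule if read literally.** Inputs from Follow up: scan at 4-6 weeks, which is day 28 to 42; calls at 6 and 12 months, each plus or minus 7 days. Assumptions: 6 months is 183 days, 12 months is 365 days, and completion means the patient's own 12-month call.

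- 12-month call: 365 - 7 = day 358 to 365 + 7 = day 372. Shortest interval 358 - 42 = 316 days (316/7 = 45.1 weeks). Longest 372 - 28 = 344 days (344/7 = 49.1 weeks).
- 6-month call: 183 - 7 = day 176 to 183 + 7 = day 190. Shortest 176 - 42 = 134 days (19.1 weeks). Longest 190 - 28 = 162 days (23.1 weeks).

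If completion means the last patient's call, the first interval is longer for patients enrolled earlier. The documents give no accrual time, so I put no number on that.

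**4. What a release could disturb.** Under Crossovers, aspirin-arm patients who "develop a new indication for periprocedural anticoagulation (e.g. perioperative atrial fibrillation) will be crossed over into the warfarin group". In the other direction: "Patients who are randomized to a warfarin group who develop contraindications to warfarin will be crossed over to the aspirin group". Each procedure has 25 patients per arm, so 25 + 25 = 50 aspirin and 50 warfarin patients are exposed to one rule or the other. One crossover is 1/25 = 4% of an arm. In the three arms with a 12-week course, about 12 - 6 = 6 to 12 - 4 = 8 weeks of treatment remain after the scan. SAVR aspirin has no end date.

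**The case against.** The strongest reply is that nobody meant this. The sentence opens as a qualification of the overt-thrombosis rule, the physicians it names are most naturally those treating the patient under that rule, and leaflet outputs are the only CT reads the protocol defines. An independent officer already reviews imaging, with no exclusion of the CT. Being independent of the care team does not forbid that officer from contacting it. Incidental-findings language often sits in consent pages, and those were removed from the file. Care also continues between study contacts, for example INR management in the warfarin arms and the end of study treatment at 12 weeks.

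Most of this stands. It rules out the stronger conclusion a reader might draw, that the trial would withhold dangerous findings from patients' doctors. The documents do not show that. They show a rule worded too broadly and no written exit from it. Inferring that the officer would act is reasonable, but the protocol does not say so, and consent text would not by itself tell the reader or officer how to act under a protocol rule without an exception.

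A reader might also take the day counts as delays in care, or as a measure of harm. They are neither; they time the literal rule between scheduled study contacts. The documents give no rate of important non-leaflet findings, so no expected number of affected patients can be given.

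Finally, a reader might suppose that releasing a non-leaflet finding could not touch the CT endpoint because the images already exist. That holds only if patients are analysed in the arm to which they were randomised. The Statistical Analysis section names no analysis set. If a crossed-over patient were counted in the new group, that patient's CT result would move with them.

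**Conclusion.** The concern holds as a minor wording gap and a cheap improvement. As worded, physicians are blinded to every 4D MDCT result until study completion, although only the leaflet-motion grade and leaflet thickness need it, and no step in the visible protocol carries an actionable non-leaflet finding to the treating physician. The officer's imaging review is a partial safeguard.

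Confidence is medium. The conclusion rests on the literal wording and on the visible text alone. The intervals of 316-344 and 134-162 days are illustrative and depend on the month lengths and the meaning of completion assumed above.

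This point does not settle whether a severe leaflet finding, such as an immobile leaflet, should ever be released. That touches the blinded outcome itself and is a separate decision for the sponsor.

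**What to change.** Replace the blinding sentence in Crossovers with wording such as:

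> Physicians will be blinded to the leaflet-motion grade and leaflet thickness from the 4D MDCT until completion of the study. Any other finding seen by the CT reader or the Medical Safety Officer that the officer judges clinically important will be passed promptly by the officer to the treating physician, without the leaflet reads, and the date logged.

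Also state whether completion is the patient's own or the last patient's 12-month call. The officer is the natural route because that role already looks at the imaging. A one-way report from the CT reader would also leave the reader blind to regimen, so this choice is partly preference. The wording covers only what is seen; it asks nobody to search beyond the leaflets. The sponsor may wish to put a time limit on prompt release, since the protocol sets no interval for the officer's review.

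**Cost.** Two sentences, a definition and a small reporting task, with no extra scans and no change in sample size. The downside is that an occasional release may trigger a crossover (4% of an arm each), if a finding made at 4-6 weeks is accepted as a periprocedural indication or a warfarin contraindication. Later clinical outcomes could then be affected. The 4-6 week CT comparison is unaffected only under analysis by randomised arm, so stating that analysis in the Statistical Analysis section would protect it.

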The need for periprocedural warfarin after bioprosthetic aortic valve replacement is uncertain. While some centers treat patients with warfarin for 6 to 12 weeks after bioprosthetic SAVR, others (including the Cleveland Clinic), employ a strategy of aspirin alone. A recent Scandinavian registry-based study suggests that short-term warfarin may improve outcomes after SAVR, but there are no large, prospective studies that validate this strategy.

Anticoagulants are also used to treat TAVR postoperatively. Typically patients will be on aspirin and clopidogrel for 12 weeks before switching them to aspirin alone. Patients who are on warfarin for atrial fibrillation may be treated with warfarin and clopidogrel for 3 months, while others are treated with aspirin and warfarin. No substantial research has shown one treatment to be more effective than the other.

The observation of reduced leaflet motion after SAVR and TAVR with the possibility of subclinical valve leaflet thrombosis has reignited the debate over periprocedural anticoagulation. The authors of the recent NEJM study point out that we need "better characterization of this observation ...to determine its frequency and evaluate its clinical effect." The purpose of this pilot trial is to determine the frequency of reduced leaflet motion after SAVR and TAVR and to determine whether perioperative anticoagulation with warfarin impacts this frequency.

Study Design

Methods: This will be a pilot prospective randomized controlled trial.

Sample: The study will enroll 50 adult patients scheduled to undergo SAVR and 50 adult patients scheduled to undergo TAVR.

Inclusion Criteria

Scheduled for SAVR or TAVR with or without the following concomitant procedures:

- Tricuspid valve surgery
- PFO closure
- ASD closure
- MV repair
- Myectomy

Age \geq 18 years

Able and willing to give informed consent

Able and willing to return for follow up

Exclusion Criteria

Contraindications to warfarin, Plavix or aspirin

Pre-existing medical indication for warfarin, Plavix or aspirin

History of previous coronary artery stenting

Requirement for concomitant coronary artery bypass grafting or mitral valve replacement

Contraindications to contrast-enhanced MDCT including anaphylactic iodine allergy, History of atrial fibrillation

Renal dysfunction (GFR < 60 ml/min).

Research Procedures

Screening

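### The closed adverse-event list names neither harms of the study contrast CT nor valve thrombosis, so foreseeable non-serious contrast harms have no clear reporting route and non-serious thrombosis is not reported as an AE

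*Combined protocol and SAP*

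**What the plan says.** The section on adverse events and the independent Medical Safety Officer sets out three categories and one review duty.

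- An AE, as defined for this pilot, is "any untoward or unfavorable medical occurrence related to structural valve deterioration, bleeding, stroke, TIA or MI".
- An Unanticipated Problem must meet three conditions together: "1) is unforeseen, (2) caused harm or placed a person at increased risk of harm, and (3) is related to the research procedures".
- An SAE "is any adverse experience that results in any of the following outcomes". The list that follows ends with a clause for important medical events, applied by medical judgment.
- The Medical Safety Officer "will routinely review all deaths, SAEs, adverse events and imaging".

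Under Contrast enhanced 4D MDCT, all subjects are scanned "after administration of iodinated contrast (80-100 mL of Ultravist 370"). The Exclusion Criteria rule out patients with contraindications to contrast CT, with anaphylactic iodine allergy as the example. They also rule out "Renal dysfunction (GFR < 60 ml/min").

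Thrombosis appears under Crossovers. Aspirin-group patients who "develop overt leaflet thrombosis, as detected by clinical standard of care imaging" may be given warfarin at the treating physician's discretion. The same section keeps physicians blinded to the 4D MDCT result until the study is complete.

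**The concern.** The AE definition is a stated rule, so the gap cannot be filled by assuming a conventional, broader definition. Two kinds of event that matter to this trial fall outside it.

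The first is harm from the contrast CT. Withholding its result from treating physicians supports reading it as a research procedure; the TTE, by contrast, is described as clinically indicated. The Introduction says the pilot is meant to inform the feasibility of a larger trial. How well patients tolerate the imaging bears on that, even though CT safety is not a stated aim.

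The second is overt valve or leaflet thrombosis, the clinical form of the condition under study. The protocol treats it as important enough to permit a change of treatment but gives it no AE category.

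**Working it through.** The main check sets the definitions against each type of event. The plan gives no figure of its own on this point.

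**Foreseeable, non-serious CT harm (contrast reaction, extravasation, clinically detected kidney injury)**

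- AE: no. None of the five listed conditions covers it.
- SAE: no, because by assumption there is no serious outcome and nobody judges it an important medical event.
- Unanticipated Problem: it meets the conditions of harm and of relation to research procedures, but it must also be unforeseen. The iodine-allergy exclusion shows that the plan foresees contrast reactions. For kidney injury the inference is weaker, since the GFR criterion is not expressly tied to contrast. Extravasation is not mentioned. The protocol does not define what counts as unforeseen, so classification depends on who reads it.
- Review of imaging: a scan does not document a reaction or a later fall in kidney function.
- Follow up: the CT is done at 4-6 weeks. That visit includes a review of medical history but no stated question on CT tolerance. The next scheduled contact is the 6-month call. The calls cover medication changes, bleeding, stroke, TIA, MI, INR results and imaging, with no contrast or kidney item.

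Result: no clear reporting route.

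**Unforeseen CT harm, serious or not.** This is an Unanticipated Problem, so it is covered.

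**Serious CT harm.** The SAE sentence speaks of any adverse experience and is not tied on its face to the AE list, so it is covered on that reading.

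**Non-serious valve or leaflet thrombosis**

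- As a finding: captured. Leaflet motion is graded on the 4D MDCT and its assessment is attempted on TTE. The 6-, 9- and 12-month calls obtain any imaging done, and the Medical Safety Officer reviews imaging.
- As an AE: not named. It could enter only if read as structural valve deterioration, a term the protocol does not define.
- The crossover rule that mentions it applies to aspirin-group patients only and creates no reporting duty.

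Result: recorded as an imaging finding, but not classified or reported to the IRB as an AE.

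**Scale of the CT gap**

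Planned scans: 50 SAVR + 50 TAVR = 100. The documents give no rate for non-serious contrast events, so r below is an assumption. Events are taken as independent with a common rate, and every enrolled patient is taken to be scanned.

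P(at least one) = 1 − (1 − r)^100

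- r = 1%: 1 − 0.99^100 = 0.634
- r = 2%: 1 − 0.98^100 = 0.867
- r = 3%: 1 − 0.97^100 = 0.952

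At every one of these rates, foreseeable non-serious events contribute zero to the AE count, because the definition excludes them.

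**The case against.** The strongest reply is that the list is deliberately targeted for a small pilot and that the other routes catch most of what matters.

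- **Thrombosis.** A reader might infer that the trial would not record non-serious thrombosis at all. The documents do not support that: suspected leaflet thrombosis is what the CT is there to look for, and the Medical Safety Officer's remit includes imaging. This part of the reply stands in full. What is missing is the AE category and the AE report.
- **SAE route.** A contrast reaction that needs treatment, or thrombosis treated with warfarin, could qualify under the important-medical-event clause. This stands, and it confines the gap to milder events and to cases where that discretion is not used.
- **Unanticipated Problem route.** The exclusions remove patients with a known risk, so a reaction in an enrolled patient might be read as unforeseen. Consent pages, which might list foreseeable risks, are not in the available text. This stands in part: the route is uncertain rather than closed. That uncertainty is itself a reason to name the events.
- **Size.** The 1-3% rates have no source in the documents. All arms have the same CT, and no estimate or comparison is shown to be affected. This stands. The figures show only that such events are plausible among 100 scans.
- **Targeted list.** A short list may suit a pilot, but one that omits harm from the study's own imaging procedure is hard to defend when naming it costs a few words.

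**Conclusion.** The concern holds in a limited form. The closed AE list leaves foreseeable, non-serious harms of the study CT without a clear reporting route. It also leaves non-serious overt thrombosis as an imaging finding with no AE classification or AE report to the IRB.

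It would be wrong to go further and say that all CT harms escape reporting, since serious events and unforeseen ones have routes.

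The conclusion rests on three readings: the AE list is exhaustive as written, the SAE definition is not restricted to that list, and the CT is a research procedure. If SAEs were instead confined to the AE list, the gap would be wider; the text leaves this open. At assumed rates of 1% to 3%, the chance that at least one non-serious contrast event occurs among 100 scans is 63% to 95%. This is a gap in safety reporting that should be corrected at low cost. It does not put the randomized comparison of leaflet motion in question.

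**What to change.** Extend the AE sentence. Keep the five conditions already listed and add valve or leaflet thrombosis, and any event related to the study MDCT (contrast reaction, extravasation, or clinically detected kidney injury). Record CT-related events at the CT visit and at the existing follow-up contacts, and tabulate them by arm and by procedure (SAVR, TAVR).

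The cost is slightly more reporting work: one longer sentence, one added question at existing contacts and a few more AE lines. No new visit or test is needed. The limit is that no laboratory test is scheduled after the CT, so kidney injury would be caught only when it comes to clinical attention. Silent falls in kidney function would still be missed, and the protocol should state this as a limitation so that a low count is not read as evidence of renal safety.

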Patients scheduled for SAVR or TAVR will be identified by nurse practice managers and their records examined to determine eligibility. Potential subjects will be contacted by a research nurse, who will determine the presence of Inclusion/Exclusion Criteria. Subjects who satisfy Inclusion/Exclusion Criteria will be approached for informed consent. Those who give informed consent will be enrolled.

Review of medical records will be done to obtain medical history.

Intra-op Aortic Valve Procedure

Randomization and Anticoagulation/Antiplatelet Regimen

After induction of anesthesia, a computer program will be used to randomize patients to one of the treatment groups below, according to their scheduled procedure:

SAVR

Warfarin group (n=25)

Warfarin treatment for 12 weeks with a target INR of 2-3 Warfarin treatment to begin on postoperative day 1-3 according to the patient's clinical status

When warfarin treatment is discontinued, patients will be treated according to standard of care (aspirin 81 mg/day) indefinitely

Aspirin group (n=25)

Aspirin (81 mg/day) to begin within 1-3 postoperative days according to the patient's clinical status and continue indefinitely per standard of care.

TAVR

Warfarin group (n=25)

Begin Warfarin and Aspirin (81 mg/day) treatment within 1-3 days postop for 12 weeks with a target INR of 2-3

At 12 weeks, study treatment will end and patients will be treated according to standard of care (aspirin 81 mg/day) indefinitely

Aspirin group (n=25)

Begin aspirin (81 mg/day) and clopidogrel (75 mg/day) in periprocedural period and continue for 12 weeks
At 12 weeks, study treatment will end and patients will be treated according to standard of care (aspirin 81 mg/day) indefinitely

A transesophageal echo (TEE) will be performed prior to implant Patients will undergo SAVR or TAVR according to standard clinical protocol.

Follow up

Patients will be seen at 4-6 weeks postoperatively for the following procedures:

- TTE
- 4D MDCT scan
- Review of medical history

At 6 months (+/- 7days), 9 months (+/- 7days) and 12 months (+/- 7days) post operatively, patients will be contacted by phone to assess for change in medications, assessment of bleeding, stroke, TIA or MI signs and symptoms, and to obtain any INR results and imaging tests if done.

Imaging

Baseline intraoperative TEE

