Periprocedural TEE will be performed to confirm normal bioprosthetic aortic valve function and establish a "valve footprint". This will include standard2D, spectral Doppler, color Doppler, full volume 3D and live 3D acquisitions. In addition, baseline aortic valve gradients will be recorded.

Transthoracic echocardiography (4-6 weeks post-procedure)

All patients will undergo a clinically indicated comprehensive TTE. Along with standard chamber dimension assessment, we will record LV outflow tract diameter in a standard fashion on parasternal long-axis view. Pulsed-wave and continuous-wave Doppler will be used to record velocities across the LV outflow tract (LVOT) and AV, respectively. AV will be examined from multiple windows including apical, suprasternal and right parasternal to obtain the peak AV velocity and the mean AV gradient. Additionally, dimensionless index will be calculated using the ratio of velocity time integral of LVOT obtained on pulse wave velocity divided by velocity time integral across aortic valve on continuous wave Doppler. AVA will be calculated using the continuity equation. In addition, attempts will be made to visualize AV leaflets and assess mobility as described below in "leaflet motion analysis".

Contrast enhanced 4D MDCT

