A statician will analyze using the following: Standard descriptive analysis will be performed. Continuous variables will be compared using t-testing or analysis of variance. Categorical variables will be compared using Chi-square. Outcomes will be compared in 2 groups using standard survival analysis. Predictors of 30-day outcomes will be determined using logistic regression analysis. All analysis will be done by standard software (SPSS and SAS). A p-value <0.05 will be considered significant.

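### A baseline valve gradient is to be recorded but no baseline adjustment is planned for the 4-6 week gradient: a possible modest loss of precision on a secondary measure, once the TEE timing is settled

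*Combined protocol and SAP*

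**What the plan says.** Under Imaging, the baseline intraoperative TEE paragraph states that "baseline aortic valve gradients will be recorded". The transthoracic echocardiography paragraph, for 4-6 weeks after the procedure, has the valve examined from several windows "to obtain the peak AV velocity and the mean AV gradient". The same kind of quantity is therefore measured twice in each patient.

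The Statistical Analysis section covers every continuous variable in one line: "Continuous variables will be compared using t-testing or analysis of variance". It names no ANCOVA, baseline covariate, change score or linear model. Its only regression is logistic, for predictors of 30-day outcomes. Gradient is not named as an endpoint anywhere.

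The protocol gives two accounts of when the TEE takes place. The Imaging section says "Periprocedural TEE will be performed to confirm normal bioprosthetic aortic valve function", which requires the new valve to be in place. The end of the randomization and regimen section says "A transesophageal echo (TEE) will be performed prior to implant".

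**The concern.** When an outcome is also measured before treatment, adjusting for the earlier value removes the part of the between-patient variation that it predicts. A plain t-test or one-way ANOVA on the follow-up value leaves that variation in the error term. Each comparison within a procedure has only 25 patients per arm, so precision is scarce, and here the covariate is one the protocol already intends to record.

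Leaving the matter open also means that the follow-up value, the change and the adjusted value could each be chosen after the data are seen.

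At stake is the width of the interval for the 4-6 week gradient and velocity comparisons. The trial's stated aims are the incidence of reduced leaflet motion and the effect of anticoagulation on it. Those rest on a binary CT classification, which this point does not touch.

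**Working it through.** The plan gives no SD, target difference or power for gradients, so there is no figure of its own to reproduce. What follows is an illustration.

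**Inputs from the documents**
- Arm size n = 25 within each procedure (randomization and regimen section). This agrees with Study Design: "The study will enroll 50 adult patients scheduled to undergo SAVR and 50 adult patients scheduled to undergo TAVR".
- Significance level 0.05 (Statistical Analysis). Sidedness is not stated; two-sided is assumed.

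**Inputs assumed**
- The correlation rho between baseline and follow-up gradient, from 0 to 0.6. Zero belongs in the range because the readings differ in modality (TEE, then TTE) and in setting (during the procedure, then at a follow-up visit), and because the baseline may turn out to be a native-valve reading.
- A true difference of 0.6 SD, chosen only to give a scale.

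**Formulas**
- Residual variance under ANCOVA, as a share of the unadjusted variance: 1 − rho².
- Equivalent unadjusted arm size: 25/(1 − rho²).
- Unadjusted power: noncentral t with 48 df and noncentrality 0.6 × √(25/2) = 2.12.
- ANCOVA power: noncentral t with 47 df. The noncentrality is divided by √[(1 − rho²)(1 + 1/46)]. The factor 1 + 1/46, that is 1 + 1/(2n − 4), is the cost of estimating the slope.

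**Results**

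| rho | Variance removed | Equivalent n per arm | Power at 0.6 SD, unadjusted | Power at 0.6 SD, ANCOVA |
|---|---|---|---|---|
| 0 | 0% | 25.0 | 54.7% | 53.8% |
| 0.3 | 9% | 27.5 | 54.7% | 57.7% |
| 0.5 | 25% | 33.3 | 54.7% | 66.0% |
| 0.6 | 36% | 39.1 | 54.7% | 72.9% |

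**Break-even.** The variance saving offsets the slope cost when (1 − rho²)(47/46) = 1. That gives rho² = 1/47 and rho of about 0.15. Below this ANCOVA loses slightly, by at most about one percentage point of power in this example.

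**Change score.** The SD of follow-up minus baseline, assuming equal SDs at the two times, is √[2(1 − rho)] times the follow-up SD. This is 1.18 at rho 0.3, 1.00 at 0.5 and 0.89 at 0.6. The ANCOVA residual SD, √(1 − rho²), is 0.95, 0.87 and 0.80. A t-test on change is therefore worse than follow-up alone below rho 0.5, and at none of these values does it match ANCOVA. It would also subtract a TEE reading from a TTE reading, whereas ANCOVA needs only that the two be correlated.

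**Which valve the baseline describes.** If the TEE confirms prosthetic function, the baseline and follow-up gradients belong to the same valve, and some correlation is plausible. If the TEE is done before implantation, the baseline belongs to a valve that is then replaced, and rho may be near zero. The documents support both readings.

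**The case against.** The strongest case against is that nothing here is an error. Randomization makes the unadjusted test unbiased with the correct type I error, and its interval already allows for chance imbalance. This is a pilot with no power claim for gradients. The stated purposes of the TEE are to check the prosthesis and provide a reference picture of it, not to supply a covariate. The size of the gain is wholly assumed, and the conflict over TEE timing could reduce it to nothing. All of this stands, and it limits the point to a possible gain in efficiency.

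A reader might infer more, in four ways that the documents do not support:

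- **That the gradient comparison is biased, or that chance imbalance invalidates it.** It is not; only precision is in question.
- **That gradient and velocity are the only continuous valve-function measures.** The TTE paragraph also lists a dimensionless index and a calculated valve area, and the leaflet motion section attempts leaflet tip thickness.
- **That a gain is assured.** At rho 0 there is a slight loss.
- **That the plan rules out any use of the baseline.** It does not say which values enter the t-test, so a change score is not excluded. A change score would be no better than ANCOVA.

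What remains after these concessions is that the plan records a reading it calls baseline, gives it no role in the analysis, and could give it one at almost no cost.

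**Conclusion.** The point holds as a modest, low-cost improvement in precision on a secondary measure. The planned comparison of 4-6 week gradient and velocity is valid but may be less efficient than the data allow. Nothing about the main outcome changes.

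The potential gain runs from none to roughly 14 extra patients per arm (39 against 25), and in the 0.6 SD example from a loss of one percentage point of power to a gain of about 18. Those bounds rest on an assumed correlation of 0 to 0.6 and an assumed difference; neither is in the documents. The upper part of the range also requires that the baseline be a reading of the implanted prosthesis, which the protocol leaves contradictory.

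**What to change.** 1. Reconcile the two statements on TEE timing. State that the baseline gradient for analysis is the reading with the prosthesis in place, taken before study treatment can affect it. The second condition needs stating because the TAVR aspirin group's regimen starts in the periprocedural period, and the protocol does not place that start relative to the TEE.
2. Then add to Statistical Analysis: 'Mean gradient and peak velocity at 4-6 weeks will be compared between arms within each procedure by ANCOVA with the baseline prosthetic gradient as covariate (on the log scale if skewed).'

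If the prosthesis-in-place reading is already part of the TEE, the cost is a few sentences and one degree of freedom per model, with no new visits or imaging. If only a native-valve gradient is recorded, little or no gain should be expected from step 2, and the data for the proposed covariate would not exist as things stand.
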